8.1.4 Early Termination of Treatment

If the subject prematurely discontinues study drug treatment, an Early Termination of Treatment (ETT) Visit should be scheduled as soon as possible after termination of study drug treatment. Subjects who prematurely discontinue treatment will also be required to complete the Safety Follow-up Visit, approximately 28 (\pm 7) days after their last dose of study drug. The assessments performed at the ETT Visit and Safety Follow-up Visit are listed in [Table 3-2](#).

The ETT Visit should occur within 7 days after the last dose of study drug. If the ETT Visit occurs 3 weeks or later following the last dose of study drug, then the ETT Visit will replace the Safety Follow-up Visit, and a separate Safety Follow-up Visit will not be required.

During the course of study conduct, if VX-661 in combination with ivacaftor is approved by local health authorities and is available for the treatment of the population enrolled in this study, subjects may be discontinued from this study at the discretion of the sponsor ([Section 10.6](#)). If a subject is continuing onto commercially available VX-661/ivacaftor, the ETT Visit will be completed before dosing with commercially available drug begins, and the Safety Follow-up Visit will not be required.

Alternatively, if after review of a marketing application, local health authorities decline to approve, or if clinically meaningful benefit is not demonstrated for the use of VX-661/ivacaftor for the treatment of CF in populations enrolled in this study, subjects within those populations may be discontinued after communication to investigators and institutional review boards (IRBs)/independent ethics committees (IECs) of the risks/benefits related to the safety and efficacy. If subjects are discontinued from the study, an ETT Visit should occur within 7 days after the last dose of study drug and a Safety Follow-up Visit should occur within 28 (\pm 7) days after the last dose of study drug.

If the subject withdraws from the study and also withdraws consent for disclosure of future information, no further evaluations should be performed and no additional data should be collected. Vertex may retain and continue to use any data collected before such withdrawal of consent.

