13.1.1.3 Documentation of Adverse Events

All AEs will be collected from the time ICF is signed until the following time points:

- For subjects who do not enroll: until time of screen failure (e.g., screen failure, withdrawal of consent)
- For enrolled subjects who have a Safety Follow-up Visit: through the Safety Follow-up Visit
- For enrolled subjects who do not have a Safety Follow-up Visit, the **earliest** of
 - 28 days after the last dose of study drug,
 - the ETT Visit, if that visit is 3 weeks or later following the last dose of study drug (see [Section 8.1.4](#)), or
 - before the first dose of study drug in another study (if applicable).

All subjects will be queried, using nonleading questions, about the occurrence of AEs at each study visit. When possible, a constellation of signs and/or symptoms will be identified as 1 overall event or diagnosis. All AEs for enrolled subjects will be recorded in the CRF and source document. AEs for subjects who are screened but not subsequently enrolled in the study will be recorded only in the subject's source documents. The following data will be documented for each AE:

- Description of the event
- Classification of “serious” or “nonserious”
- Date of first occurrence and date of resolution (if applicable)
- Severity
- Causal relationship to study drug(s)
- Action taken
- Outcome
- Concomitant medication or other treatment given

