2. If there is more than one measurement available within the same visit window, use the following rules:

For all efficacy parameters, if there are multiple measurements within a visit window, the record at the scheduled visit will be used. Otherwise,

- If there are no measurements at the scheduled visit, then the record closest to the target day will be used;

- If there are multiple records with the same distance to the target day, the latest record will be used.
- Assessments at early treatment termination (ETT) visit will follow the windowing rules for regular visits up to Week 72.
- Assessments at safety follow-up (SFU) visit will follow the windowing rules for regular visits if it falls within the upper boundary of the window for Week 72, or remain as SFU if it goes beyond the upper boundary of the window for Week 72.

For all safety parameters, if there are multiple measurements within a visit window, then 1) the record closest to the target day will be used; 2) if there are multiple records within the same distance from the target day, the latest record will be used; or 3) SFU visit will not be windowed, instead, used per nominal visit in relevant analyses.

Incomplete/Missing data will not be imputed, unless otherwise specified.

Outliers: No formal statistical analyses will be performed to detect or remedy the presence of statistical outliers, unless otherwise specified.

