10.2 Appendix B: Analysis Visit Window Mapping Rules for Efficacy and Safety Measurements

Table 10-3 Visit Window Mapping Rules

Assessments	Visit	Target Study Day	Visit Window (in study days)
Standard 12-lead ECG Vital signs Pulse oximetry Serum Chemistry	Baseline	1	≤1
	Day 15	15	[2, 22]
	Week 4	29	[23, 57]
	Week 12	85	[58, 127]
	Week 24	169	[128, 211]
	Week 36	253	[212, 295]
	Week 48	337	[296, 379]
	Week 60	421	[380, 463]
	Week 72	505	[464, 519]
	ETT	N/A	Follow the individual visit window to be mapped to individual visits
Safety Follow-up Visit	N/A	Nominal	
Hematology Lipid and Vitamin Levels	Baseline	1	≤1
	Week 24	169	[2, 253]
	Week 48	337	[254, 421]
	Week 72	505	[422, 519]
	ETT	N/A	Follow the individual visit window to be mapped to individual visits
	Safety Follow-up Visit	N/A	Nominal
Coagulation	Baseline	1	≤1
	Week 72	505	[464, 519]
	Safety Follow-up Visit	N/A	Nominal

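### An ETT Visit held 3 weeks or more after the last dose replaces the Safety Follow-up Visit in the protocol, but the SAP reports its safety data under a scheduled treatment visit

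*SAP*

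**What the plan says.** Protocol 8.1.4 sets the normal timing: "The ETT Visit should occur within 7 days after the last dose of study drug". It also provides for a late visit: "If the ETT Visit occurs 3 weeks or later following the last dose of study drug", "the ETT Visit will replace the Safety Follow-up Visit", and no separate follow-up visit is held. Protocol 13.1.1.3, on when adverse event collection ends, names this case ("the ETT Visit, if that visit is 3 weeks or later following the last dose of study drug") under enrolled subjects who have no Safety Follow-up Visit. The record therefore keeps its ETT label.

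For safety parameters, SAP 8.1 says "SFU visit will not be windowed, instead, used per nominal visit in relevant analyses". That section's own sentence on ETT records, "Assessments at early treatment termination (ETT) visit will follow the windowing rules for regular visits up to Week 72", stands among the efficacy rules. For safety data the ETT rule is in Table 10-3 (Appendix B). The ETT row there reads "Follow the individual visit window to be mapped to individual visits". It applies to ECG, vital signs, pulse oximetry and serum chemistry, and again to hematology and lipid and vitamin levels. Coagulation has no ETT row.

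When a safety window holds several records, SAP 8.1 takes the one closest to the target day, and the later one on a tie. Unscheduled records compete in the same windows.

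**The concern.** The protocol treats a late ETT Visit as the follow-up visit. The SAP has no matching rule and decides by visit label alone. A subject seen 25 days after the last dose is summarized under Safety Follow-up if the visit carries that name. If it is called ETT, the subject is summarized under Week 12, Week 24 or another treatment visit.

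What is at stake is what the by-visit safety output means. Values taken three to four weeks off drug would sit in the treatment-visit means, threshold counts and liver test box plots, and would be missing from the follow-up results. In some cases such a value could also be chosen over an on-drug value in the same window.

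**Working it through.** **Inputs**
- Late ETT: 21 or more days after the last dose (Protocol 8.1.4).
- Windows and targets: SAP Table 10-3.
- Selection rule, and end of the treatment-emergent (TE) period at 28 days after the last dose when there is neither a Safety Follow-up Visit nor rollover: SAP 8.1.
- Visit tolerances of 7 days (3 days at Day 15) and the sampling schedule: Protocol Table 3-2.

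**1. Reproducing the windows.** Each boundary is the midpoint between consecutive targets, and the last upper bound is target + 14. Week 24 chemistry: lower (85 + 169)/2 + 1 = 128, upper (169 + 253)/2 = 211. Week 72: 505 + 14 = 519. Hematology Week 24: upper (169 + 337)/2 = 253. All eight windows of the first set and all three of the hematology and lipid/vitamin set match the table.

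**2. Where a late ETT lands.** Take last-dose days 1 to 503 and gaps of 21 to 28 days, which is 503 × 8 = 4024 combinations. The ETT falls after Day 519 in 5 + 6 + … + 12 = 68 of them. The other 4024 − 68 = 3956 (98.3%) land in a Day 15 to Week 72 window of the first set. Of these, 2604 fall in the window that contains the last dose and 1352 in a later one. The 68 have no analysis visit at all. These are counts of calendar combinations, not probabilities.

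**3. Mislabelling example.** Last dose Day 60, ETT Day 85.
- Off drug for 85 − 60 = 25 days. The TE period ends on Day 60 + 28 = 88, so the visit is inside it.
- Hematology: Day 85 lies in [2, 253], and no hematology draw is scheduled between Day 1 and Week 24. Unless an unscheduled sample lies closer to target, this becomes the Week 24 value, although it is 169 − 85 = 84 days before target.
- Chemistry and ECG from the same visit become Week 12 ([58, 127], target 85).
- Labelled Safety Follow-up, the same visit would enter no window.

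**4. When an on-drug record can be displaced.** Let d be the day of the on-drug record, t the target and e the ETT day. Assessments are made before dosing, so the last dose is on day d − 1 or later and e ≥ d − 1 + 21 = d + 20. Displacement needs |e − t| ≤ |d − t|. With d before t, d + 20 − t ≤ t − d, so d ≤ t − 10. With d at or after t it cannot occur.
- A scheduled visit inside its 7-day or 3-day tolerance is therefore never displaced. Only an unscheduled sample or a visit held well before its tolerance can be.
- Week 4: d ≤ 19 lies below the window start of 23, so displacement is impossible. Day 15: one combination only (record Day 2, last dose Day 1, ETT Day 22).
- Displaced: unscheduled sample Day 140 (29 days from 169), last dose Day 147, ETT Day 170 (23 days off drug, 1 day from target). Week 24 takes the ETT value.
- Not displaced: scheduled visit Day 169, last dose Day 176, ETT Day 197 (21 days off drug, 28 days from target). Week 24 keeps the on-drug value.

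**5. More than 28 days after the last dose.** The by-visit safety summaries use treatment-emergent data. If a replacing ETT is not a Safety Follow-up Visit for the TE definition, a record after day 28 drops out of them. If it is one, the TE period runs to that record and it is windowed. The SAP does not say which, so the clear exposure is 21 to 28 days.

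**6. After the change.** With ETT records at 21 or more days kept nominal, none enters a treatment-visit window and none can displace an on-drug record.

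**The case against.** Mapping by study day is an explicit, prespecified choice, and a Week 24 label can fairly mean time since first dose rather than time on drug. That would settle the matter if the SAP applied it to both labels. For safety data it exempts the Safety Follow-up Visit and not the ETT Visit that replaces it, so the inconsistency remains. The SAP gives no reason for the exemption; that it is there because the visit is off treatment is an inference.

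Other limits are real. ETT Visits are meant to occur within 7 days, and the documents do not say how many will be late. Safety is descriptive, with no testing. ETT Visits up to 20 days off drug would stay windowed under the change proposed here; the line at 21 days is the protocol's own.

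A reader might go further in three ways that the documents do not support.
- *That an on-drug liver peak would be hidden.* Suppose ALT is 9 × ULN on Day 140 and normal at an ETT on Day 165. The ETT wins Week 24 (4 days from target against 29). But Protocol 11.6.3 calls for repeat testing within 48 to 72 hours, and those samples are windowed too. Days 142 and 143 are 27 and 26 days from target, so they already beat Day 140. Relabelling the ETT would not put 9 × ULN into Week 24. The peak stays in the TE-period maxima and threshold counts, and in the listing of subjects with elevated liver tests.
- *That subjects who stop for liver or ECG findings are the ones with late ETT Visits.* Nothing says so, and Protocol 11.6.3 and 11.6.5 require close monitoring of these subjects.
- *That the TE period should simply run to the late ETT date.* Protocol 13.1.1.3 ends adverse event collection for these subjects at the earliest of several dates, among them 28 days after the last dose and the late ETT. With an ETT on day 40, the TE period would outlast adverse event collection by 40 − 28 = 12 days.

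**Conclusion.** The point holds in a limited form. A protocol rule has not been carried into the SAP, and following the SAP as written reports the same off-drug visit differently according to its label. The affected output is the by-visit summaries of ECG, vital signs, oximetry, chemistry, hematology, and lipids and vitamins, together with the follow-up results from which the visit is missing.

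The main effect is mislabelling, which needs no competing record. Displacement of an on-drug value is a narrower addition. One affected subject is 1/20 = 5 percentage points in a by-visit threshold count if all 20 subjects in the arm contribute, and more if fewer do. The total effect cannot be sized without the number of late ETT Visits.

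The primary endpoint is unaffected: no CT scan is scheduled at ETT. The conclusion assumes that a replacing visit keeps its ETT label in the database, as the wording of Protocol 13.1.1.3 implies. It is worth correcting before database lock because the remedy is so cheap, not because a safety signal would be lost.

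**What to change.** In SAP 8.1 (safety parameters) and the ETT rows of Table 10-3, state that safety assessments from an ETT Visit 21 or more days after the last dose are reported as Safety Follow-up, nominal and not windowed. Keep the present windowing for earlier ETT Visits. This also gives an analysis visit to late ETT records after Day 519.

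Separately, state in the TE definition whether a replacing ETT counts as the Safety Follow-up Visit. Whichever is chosen, keep it consistent with the adverse event collection cut-off in Protocol 13.1.1.3, and do not let the TE period run to the late ETT date without limit.

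The cost is a few sentences in the SAP and a small programming change, with no new data. The downside is slightly fewer records in the by-visit treatment summaries.

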10.3 Appendix C: Imputation Rules for Missing Prior/Concomitant Medication Dates

As an intermediate step for programming purposes, medications with missing or partially missing start dates will use 2000 to impute a missing year, January for a missing month, and 1 for a missing day. Medications with missing or partially missing stop dates will use 2050 to impute for a missing year, December for a missing month, and the last day of the month for a missing day. The logic to decide the category of a medication is presented in Table 10-4:

Table 10-4 Logic for Determining the Category of a Medication

Medication start date	Medication end date		
	< first dose date of study drug	≥ first dose date and ≤ End date of TE period	> End date of TE period
< first dose date of study drug	P	PC	PCA
≥ first dose date and ≤ End date of TE period	-	C	CA
> End date of TE period	-	-	A

P: Prior; C: Concomitant; A: Post

10.4 Appendix D: Coefficients for Hankinson and Wang Methods for Calculating Predicted Spirometry Parameters

Percent predicted FEV₁ is the ratio of FEV₁ (L) to the predicted FEV₁ (L), expressed as a percentage. The predicted FEV₁ (L) will be calculated using the Hankinson² and Wang³ standards.

The Hankinson standard will be applied to male subjects 18 years and older and female subjects 16 years and older; the Wang standard will be applied to male subjects 6 to 17 years and female subjects 6 to 15 years of age. During the study, the subjects who have a birthday that would move them from Wang to Hankinson will use the Wang standard before that birthday and the Hankinson standard at or after that birthday.

Hankinson Normal Values (HNVs) will be calculated for FEV₁, forced vital capacity (FVC), forced expiratory flow mid expiratory phase (FEF_{25-75%}), and FEV₁/FVC% using the Hankinson equation:

$$\text{Predicted lung function parameter} = b_0 + b_1 \times \text{age} + b_2 \times \text{age}^2 + b_3 \times \text{height}^2$$

In the equation, height is given in centimeters, age is given in years, and the coefficients b₀, b₁, b₂, and b₃ are determined based on subject's sex, race, and age group as shown in [Table 10-5](#).

Wang Normal Values (WNVs) will be calculated for FEV₁, FVC, FEF_{25-75%}, and FEV₁/FVC using the Wang equation:

$$\ln(\text{Predicted lung function parameter}) = \alpha + \beta \ln(\text{height})$$

Wang Normal Values (WNVs) will be calculated for FEV₁, FVC, FEF_{25-75%}, and FEV₁/FVC using the Wang equation. In the equation, height is given in meters, and the coefficients α and β are determined based on subject's sex, race, and age as shown in [Table 10-6](#) and [Table 10-7](#).

Table 10-5 HNVs Equation Coefficients by Sex, Race, and Age

Parameter	Sex	Race	Age		b_0	b_1	b_2	b_3
			(years)					
HNV _{FEV1}	Male	Caucasian	<20		-0.7453	-0.04106	0.004477	0.00014098
			≥20		0.5536	-0.01303	-0.000172	0.00014098
		African American	<20		-0.7048	-0.05711	0.004316	0.00013194
			≥20		0.3411	-0.02309		0.00013194
		Mexican American	<20		-0.8218	-0.04248	0.004291	0.00015104
			≥20		0.6306	-0.02928		0.00015104
	Female	Caucasian	<18		-0.8710	0.06537		0.00011496
			≥18		0.4333	-0.00361	-0.000194	0.00011496
		African American	<18		-0.9630	0.05799		0.00010846
			≥18		0.3433	-0.01283	-0.000097	0.00010846
		Mexican American	<18		-0.9641	0.06490		0.00012154
			≥18		0.4529	-0.01178	-0.000113	0.00012154
HNV _{FVC}	Male	Caucasian	<20		-0.2584	-0.20415	0.010133	0.00018642
			≥20		-0.1933	0.00064	-0.000269	0.00018642
		African American	<20		-0.4971	-0.15497	0.007701	0.00016643
			≥20		-0.1517	-0.01821		0.00016643
		Mexican American	<20		-0.7571	-0.09520	0.006619	0.00017823
			≥20		0.2376	-0.00891	-0.000182	0.00017823
	Female	Caucasian	<18		-1.2082	0.05916		0.00014815
			≥18		-0.3560	0.01870	-0.000382	0.00014815
		African American	<18		-0.6166	-0.04687	0.003602	0.00013606
			≥18		-0.3039	0.00536	-0.000265	0.00013606
		Mexican American	<18		-1.2507	0.07501		0.00014246
			≥18		0.1210	0.00307	-0.000237	0.00014246
HNV _{FEF25-75%}	Male	Caucasian	<20		-1.0863	0.13939		0.00010345
			≥20		2.7006	-0.04995		0.00010345
		African American	<20		-1.1627	0.12314		0.00010461
			≥20		2.1477	-0.04238		0.00010461
		Mexican American	<20		-1.3592	0.10529		0.00014473
			≥20		1.7503	-0.05018		0.00014473
	Female	Caucasian	<18		-2.5284	0.52490	-0.015309	0.00006982
			≥18		2.3670	-0.01904	-0.000200	0.00006982
		African American	<18		-2.5379	0.43755	-0.012154	0.00008572
			≥18		2.0828	-0.03793		0.00008572
		Mexican American	<18		-2.1825	0.42451	-0.012415	0.00009610
			≥18		1.7456	-0.01195	-0.000291	0.00009610
HNV _{FEV1/FVC%}	Male	Caucasian			88.066	-0.2066		
		African American			89.239	-0.1828		
		Mexican American			90.024	-0.2186		
	Female	Caucasian			90.809	-0.2125		
		African American			91.655	-0.2039		
		Mexican American			92.360	-0.2248		

Source: Reference (Hankinson JL, 1999) (Tables 4, 5 and 6)

Table 10-6 WNVs Equation Coefficients by Sex and Age in White Boys and Girls

Sex	Age	FEV ₁		FVC		FEF _{25-75%}		FEV ₁ /FVC	
		α	β	α	β	α	β	α	β
Male	6	-0.109	2.252	-0.024	2.470			-0.078	-0.248
	7	-0.104	2.270	-0.018	2.489			-0.086	-0.220
	8	-0.089	2.257	0.005	2.443	0.264	1.505	-0.091	-0.199
	9	-0.063	2.197	0.017	2.426	0.308	1.443	-0.086	-0.206
	10	-0.057	2.212	0.030	2.407	0.290	1.557	-0.081	-0.209
	11	-0.093	2.324	0.009	2.468	0.242	1.738	-0.101	-0.147
	12	-0.161	2.512	-0.061	2.649	0.165	1.982	-0.101	-0.133
	13	-0.292	2.843	-0.175	2.924	0.007	2.396	-0.116	-0.085
	14	-0.329	2.983	-0.219	3.060	0.014	2.483	-0.106	-0.087
	15	-0.141	2.709	-0.079	2.859	0.241	2.163	-0.060	-0.155
	16	0.062	2.409	0.104	2.591	0.503	1.764	-0.045	-0.178
17	0.262	2.099	0.253	2.374	0.762	1.368	0.008	-0.272	
Female	6	-0.109	1.949	-0.013	2.007			-0.097	-0.055
	7	-0.144	2.243	-0.062	2.385			-0.084	-0.132
	8	-0.137	2.239	-0.055	2.381	0.247	1.668	-0.079	-0.152
	9	-0.123	2.222	-0.039	2.351	0.254	1.710	-0.084	-0.128
	10	-0.161	2.364	-0.068	2.458	0.195	1.933	-0.092	-0.097
	11	-0.223	2.558	-0.120	2.617	0.161	2.091	-0.102	-0.061
	12	-0.264	2.709	-0.174	2.776	0.185	2.120	-0.090	-0.067
	13	-0.153	2.535	-0.061	2.576	0.294	1.976	-0.093	-0.040
	14	0.046	2.178	0.139	2.208	0.450	1.711	-0.096	-0.026
	15	0.148	2.008	0.210	2.099	0.581	1.486	-0.062	-0.093

Source: Reference (Wang X, 1993) (Tables 2 and 3)

Table 10-7 WNVs Equation Coefficients by Sex and Age in Black Boys and Girls

Sex	Age	FEV ₁		FVC		FEF _{25-75%}		FEV ₁ /FVC	
		α	β	α	β	α	β	α	β
Male	6	-0.166	1.723	-0.088	1.961			-0.091	-0.152
	7	-0.122	1.846	-0.040	2.040			-0.091	-0.153
	8	-0.225	2.271	-0.094	2.323	0.097	1.544	-0.118	-0.104
	9	-0.142	2.059	-0.074	2.308	0.255	1.248	-0.079	-0.218
	10	-0.157	2.117	-0.110	2.417	0.230	1.428	-0.047	-0.303
	11	-0.176	2.166	-0.138	2.453	0.256	1.438	-0.048	-0.263
	12	-0.307	2.548	-0.224	2.710	0.085	1.936	-0.084	-0.162
	13	-0.486	2.962	-0.342	2.975	-0.121	2.476	-0.141	-0.018
	14	-0.472	3.010	-0.337	3.035	-0.115	2.536	-0.123	-0.050
	15	-0.318	2.789	-0.226	2.889	0.170	2.120	-0.070	-0.140
	16	0.074	2.140	0.058	2.425	0.663	1.299	0.018	-0.289
	17	0.053	2.223	0.148	2.310	0.505	1.618	-0.095	-0.087
Female	6	-0.288	2.182	-0.172	2.117			-0.109	0.059
	7	-0.250	2.158	-0.135	2.132			-0.104	-0.030
	8	-0.276	2.295	-0.176	2.362	-0.283	2.990	-0.103	-0.066
	9	-0.294	2.330	-0.200	2.452	0.025	2.062	-0.097	-0.104
	10	-0.344	2.507	-0.230	2.571	0.051	2.028	-0.120	-0.043
	11	-0.308	2.460	-0.204	2.526	0.078	2.006	-0.089	-0.105
	12	-0.219	2.312	-0.107	2.342	0.225	1.804	-0.115	-0.021
	13	-0.117	2.196	-0.042	2.294	0.418	1.504	-0.051	-0.148
14	0.041	1.920	0.105	2.021	0.574	1.257	-0.063	-0.103	
15	0.203	1.662	0.253	1.787	0.599	1.281	-0.043	-0.139	

Source: Reference (Wang X, 1993) (Tables 4 and 5)

10.7 Appendix G: Imputation Rules for Missing AE Start Dates

For missing or partial AE start date, use the imputation rules below.

If only Day of AE start date is missing:

If the AE start year and month are the same as that for the first dose date, then:

If the full (or partial) AE end date is NOT prior to the first dose date or AE end date is missing, then impute the AE start day as the day of first dose date; otherwise, impute the AE start day as 1.

Otherwise, impute the AE start day as 1.

Compare the imputed AE start date with TE period to determine whether the AE is pre-treatment AE, TEAE or post-treatment AE.

If Day and Month of AE start date are missing:

If AE start year = first dose year, then:

If the full (or partial) AE end date is NOT prior to the first dose date or AE end date is missing, then impute the AE start Month and Day as the Month and Day of first dose date; otherwise, impute the AE start Month as January and the Day as 1.

Otherwise, impute the AE start Month as January and the Day as 1.

Compare the imputed AE start date with TE period to determine whether the AE is pre-treatment AE, TEAE or post-treatment AE.

If Year of AE start date is missing:

If the year of AE start is missing or AE start date is completely missing then query site with no imputation. Also compare the full (or partial) AE end date to the first dose date. If the AE end date is prior to the first dose date then the AE should be considered as a pre-treatment AE. Otherwise, the AE will be considered as TEAE.

